8.1 ANALYSIS OF PRIMARY IMMUNOGENICITY ENDPOINT

The primary immunogenicity analysis will be a comparison of geometric mean titres (GMTs) for SARS-CoV-2 neutralizing antibodies at 14 days after the second dose (i.e. Day 36).

GMTs along with corresponding 95% CI will be estimated by applying analysis of variance (ANOVA) for \log_{10} transformed neutralizing antibody titre including the factors dose group and study site. Estimates (least squares means, least squares means differences and the corresponding 95% CIs) obtained from ANOVA will be back transformed (antilog_{10}) to get the estimates of GMT, and corresponding 95% CI. If ANOVA suggests dose group differences to be statistically significant then Tukey’s HSD test will be applied for pair wise comparisons of dose groups. The table will also include the following descriptive summary statistics: number of non-missing observations (n), median, minimum, maximum.

If \log_{10} transformed data is not normally distributed then GMTs (CI) will be calculated by taking the antilogarithm of the mean (CI) of the \log_{10} transformed titre. Also p-value from Kruskal Wallis test will be calculated to check if the results are significantly different among dose groups at 5% level of significance. If the test suggests significant p-value then pairwise group comparison will be performed using Dwass, Steel, Critchlow-Fligner (DSCF) multiple comparisons post-hoc procedure to determine which pair of dose groups differ significantly.

In addition, as an exploratory analysis, data for SARS-CoV-2 neutralizing antibodies for an external convalescent group of participants will be presented. All dose groups will also be compared with this group.

A graph overlaying scatter plot over box plots for SARS-CoV-2 neutralizing antibodies titres will be presented by visits and dose cohorts. Similar scatter plot will be presented for convalescent participants also.

In addition, reverse cumulative distribution functions will be plotted for SARS-CoV-2 neutralizing antibodies titres (ND50) by dose groups for scheduled visits Day 1, 8, 22, 36, 106, 208.

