## **14. ASSESSMENT OF IMMUNOGENICITY**

All serum samples obtained for the determination of neutralizing antibodies and IgG antibodies against SARS-CoV-2 will be handled according to the procedures supplied to each investigative site for the preparation, storage and shipment of samples (refer to Laboratory Manual). Immunogenicity samples will be collected from all Participants at the time points indicated in section 22.2 and 22.3. Each clinical study site will be responsible for the separation of serum from whole blood samples and the safe and controlled storage of serum samples prior to shipment to the central laboratory.

Immunogenicity sample (10ml) will be drawn for SARS-CoV-2-specific neutralizing antibody titre evaluation and ELISA antibody titre evaluation.

Serum samples to measure SARS-CoV-2 neutralizing antibody levels will be collected from Participants on Day 1 (prior vaccination), Day 8, Day 22 (prior vaccination), Day 36, Day 106 and Day 208. An authorized laboratory will measure neutralizing antibodies to SARS-CoV-2 using wild-type virus neutralizing assay. In addition to the functional assays, samples will be analysed for IgG against SARS-CoV-2 by ELISA.

The cell-mediated immune response (T-cell response) will be assessed on Day 1, Day 36 and Day 208 by characterizing PBMCs; methods may include T-cell ELISpot assays to SARS-CoV-2 antigens.

Booster Phase:

During the Booster Phase, a blood sample (10 ml) will be collected at Visit 7 (before vaccination), Visit 8 and Visit 9, to measure SARS-CoV-2-specific neutralizing antibody titre and ELISA antibody titre.

Similarly, cell-mediated immune response (T-cell response) will be assessed by characterizing PBMCs at Visit 7 and Visit 8.

More details about the Booster Phase assessments can be found in section 22.3.

At the end of the study, results of immunogenicity assessments will be provided to the Investigator.

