### **16.4.2 Primary Immunogenicity Endpoint**

The primary immunogenicity analysis will be a comparison of GMTs for SARS-CoV-2 neutralizing antibodies at 14 days after the second dose (i.e. Day 36).

Therefore, GMTs and GMT ratios will be estimated by applying an analysis of variance (ANOVA) including the factor treatment group and study site. This will be done using log10 transformed data and taking the anti-log of the resulting point estimates for the least squares means, least squares means differences and the corresponding 95% CIs. Tukey's HSD test will be applied for pair wise comparisons.

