6.2 DEMOGRAPHICS AND BASELINE CHARACTERISTICS

Descriptive statistics of the demographic and baseline characteristics for each dose group and overall will be presented for safety analysis set. The following demographic and baseline characteristics will be summarized:

- Age at the time of informed consent (years)
- Sex
- Childbearing potential and reason for no childbearing potential
- Ethnicity
- Height at screening (cm)
- Weight at screening (kg)
- Body Mass Index (BMI) at screening (kg/m²)
- COVID-19 Test Result at screening (Positive, Negative)
- HBsAg Test Result at screening (Positive, Negative)
- HCV Test Result at screening (Positive, Negative)
- HIV Test Result at screening (Positive, Negative)

All demographic and baseline data will also be listed.

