8 IMMUNOGENICITY ANALYSES

Immunogenicity samples (10ml) will be drawn for SARS-CoV-2-specific neutralizing antibody titre evaluation using wild-type virus microneutralization assay (WT-MNA) and binding IgG antibody titre evaluation by ELISA. In addition, a blood sample [approx. 50mL] will be collected to isolate PBMCs from all participants except sentinel participants for future investigation of cellular immune responses to VLA2001.

Serum samples to measure SARS-CoV-2 neutralizing antibody levels will be collected from participants on Day 1 (prior first vaccination), Day 8, Day 22 (prior second vaccination), Day 36, Day 106 and Day 208. An authorized laboratory will measure virus specific neutralizing antibodies to SARS-CoV-2 using wild-type virus microneutralizing assay (WT-MNA). In brief, infectious virus is incubated with sera. Virus susceptible cell monolayers are exposed to the test sera/virus mixture. Patches of infected cells (microplaques) are detected via an antibody pair specific for the SARS-CoV-2 RBD Spike protein and visualised using colored substrate. Neutralizing titer of test sera is expressed as ND₅₀; serum dilution at where 50% of virus is neutralized. The Part A Day 36 analysis was performed with values below the limit of quantification of the WT-MNA (ND₅₀=58; i.e titre <58) before the WT-MNA was fully validated and LLOQ values were replaced with a value of 29 (i.e LLOQ/2=29). All subsequent analyses are performed with values below the limit of quantification of the fully validated WT-MNA (ND₅₀=62; i.e titre <62) and values lower than LLOQs will be replaced by 31 (LLOQ/2= 31). For results given as e.g. ND₅₀>SDUL reported value will be replaced with the highest sample dilution tested (SDUL) in all analyses..

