In addition to the functional assays, samples are analysed for IgG against SARS-CoV-2 by a human anti-SARS-CoV-2 pre-spike IgG antibody ELISA (S-ELISA). In brief, the SARS-CoV-2 pre-spike recombinant antigen is adsorbed onto the 96-well microplate. Dilution series of human sera, standard and controls are added to microtitre plates coated with the SARS-CoV-2 pre-spike recombinant antigen. Presence of binding IgGs is detected with an anti-human IgG antibody conjugated to peroxidase, followed by addition of the peroxidase substrate. The optical density of the colored end product is proportional to the amount anti-SARS-CoV-2 pre-spike IgG antibodies present in the serum sample. Values below the quantitation limit of the ELISA (50.3 ELU/mL) and samples scored

as “negative” will be replaced by 25 ELU/mL. Also values above the quantitation limit (>15798 ELU/mL) will be replaced by 15798 ELU/mL.

Immunogenicity analysis will be presented for the respective PPAS and modified PPAS population. In addition analysis can also be presented for FAS population. Immunogenicity analysis may also be presented for “Unscheduled COVID-19 illness visit” that will be performed if a participant tests positive for COVID-19 during the study.

Immunogenicity analysis may also be presented stratified for MNA positive/negative at Visit 1. MNA result will be considered positive if result (ND50) \geq LLOQ, i.e. ≥ 62 . Otherwise if the result (ND50) $<$ LLOQ then MNA will be considered negative.

All secondary immunogenicity analysis for booster phase will be presented by primary treatment group (Low Dose/ Medium Dose/ High Dose) of participant and the tables will also be presented stratified by following factors: Received other COVID-19 vaccine any time during study / Not received other COVID-19 vaccine any time during study/ COVID-19 positive any time during study who did not receive other COVID-19 vaccine any time during study.

Immunogenicity analysis will also be presented for participants in PPAS and mPPAS who received a booster dose.

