13.4 INDEX OF FIGURES

Figure	Title	Population	Included in Interim Part A Analysis?	Included in Second Interim Analysis?	Included in Third Interim Analysis?
1.1.1	Solicited Adverse Events Within 7 Days After First Vaccination	Safety	Yes	Yes	No
1.1.2	Solicited Adverse Events Within 7 Days After Second Vaccination	Safety	Yes	Yes	No
1.1.3	Solicited Injection Site Reactions Within 7 Days After First Vaccination	Safety	Yes	Yes	No
1.1.4	Solicited Systemic Reactions Within 7 Days After First Vaccination	Safety	Yes	Yes	No
1.1.5	Solicited Injection Site Reactions Within 7 Days After Second Vaccination	Safety	Yes	Yes	No
1.1.6	Solicited Systemic Reactions Within 7 Days After Second Vaccination	Safety	Yes	Yes	No
1.2.1	Plot of SARS-CoV-2 Neutralizing Antibodies (ND50) Over Time by Dose Groups	Per-Protocol	Yes	Yes	Yes
1.2.1.1	Plot of SARS-CoV-2 Neutralizing Antibodies (ND50) Over Time by Dose Groups	Modified Per-Protocol	Yes	Yes	Yes

1.2.2	Plot of SARS-CoV-2 Neutralizing Antibodies (ND50) for Convalescent Sera	All Convalescent Participants	Yes	Yes	No
1.2.3	Plot of SARS-CoV-2 Neutralizing Antibodies (ND50) Over Time by Dose Groups for MNA Positive Participants at Visit 1	Per-Protocol	Yes	Yes	Yes
1.2.3.1	Plot of SARS-CoV-2 Neutralizing Antibodies (ND50) Over Time by Dose Groups for MNA Positive Participants at Visit 1	Modified Per-Protocol	Yes	Yes	Yes
1.2.4	Plot of SARS-CoV-2 Neutralizing Antibodies (ND50) Over Time by Dose Groups for MNA Negative Participants at Visit 1	Per-Protocol	Yes	Yes	Yes
1.2.4.1	Plot of SARS-CoV-2 Neutralizing Antibodies (ND50) Over Time by Dose Groups for MNA Negative Participants at Visit 1	Modified Per-Protocol	Yes	Yes	Yes
1.3	Plot of S-protein specific IgG Antibody Titres (ELISA) Over Time by Dose Groups	Per-Protocol	Yes	Yes	Yes
1.4.1	Plot of IFNgamma Spot Forming Units per 2.5×10^5 PBMC by Dose Groups and Assessment Days for Panel 1 Spike Protein N Terminus	Per-Protocol	Yes	Yes	Yes
1.4.2	Plot of IFNgamma Spot Forming Units per 2.5×10^5 PBMC by Dose Groups and Assessment Days for Panel 2 Spike Protein C terminus	Per-Protocol	Yes	Yes	Yes
1.4.3	Plot of IFNgamma Spot Forming Units per 2.5×10^5 PBMC by Dose Groups and Assessment Days for Panel 3 Nucleocapsid Protein	Per-Protocol	Yes	Yes	Yes
1.4.4	Plot of IFNgamma Spot Forming Units per 2.5×10^5 PBMC by Dose Groups and Assessment Days for Panel 4 Membrane Protein	Per-Protocol	Yes	Yes	Yes

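### The primary GMT comparison leaves out Day 1 titre and age, and the SAP commits to no adjusted or stratified GMT ratio should baseline-positive participants be unevenly spread across dose groups

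*SAP*

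**What the plan says.** SAP 8.1 estimates GMTs and their ratios from an ANOVA on log10 neutralising titre "including the factors dose group and study site". Protocol 16.4.2 specifies the same model, "including the factor treatment group and study site". If the log10 titres are not normal, SAP 8.1 falls back to Kruskal-Wallis with pairwise rank comparisons, which drops site as well.

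The baseline values exist. Protocol 14 states that "Immunogenicity samples will be collected from all Participants at the time points indicated in section 22.2 and 22.3", and the schedule in 22.2 includes Day 1. SAP 6.2 lists age among the baseline characteristics, and age is not used further.

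Baseline antibody status is treated in several places:

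- Protocol 16.4.3.2 plans to repeat the immunogenicity analysis by serostatus at screening.
- SAP 13.1 withdraws that stratification, because exclusion criterion 2 is taken to make the chance of enrolling seropositive participants negligible.
- SAP 8 keeps an option: "Immunogenicity analysis may also be presented stratified for MNA positive/negative at Visit 1".
- SAP 13.4 indexes figures by that status, including one titled in part "Over Time by Dose Groups for MNA Positive Participants at Visit 1", for all three interim analyses.
- SAP 8.2.2 limits seroconversion to participants negative for SARS-CoV-2 infection at screening.
- SAP 8.2.3 and 8.2.6 analyse the fold increase from Day 1 (GMFI) with the same ANOVA.

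**The concern.** The reason given in SAP 13.1 does not fully close the gap. Exclusion criterion 2 (synopsis wording) bars a history of laboratory-confirmed infection. Antibody serology is drawn at screening (protocol 15.7), but no exclusion criterion names a positive antibody result, so someone with an undiagnosed past infection is not clearly excluded. The mPPAS in SAP 4.4 removes only participants testing positive after the first vaccination, so a participant already positive on Day 1 stays in both per-protocol sets.

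Such participants may respond more strongly at Day 36. They would then add residual variance to the dose contrast and, if unevenly spread over groups of about 45, move a GMT ratio. Seroconversion has a guard against this. The primary GMT ratio has only descriptive figures, an optional stratification and a related secondary endpoint. Adjusting for values measured before vaccination costs almost nothing.

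**Working it through.** **Inputs from the documents.** Fifty per group with 10% protocol deviations (protocol 16.1, SAP 2.5): 50 × (1 − 0.10) = 45 evaluable, which reproduces the stated figure. The documents give no SD of log10 titre, share of baseline positives, size of their Day 36 shift, or age slope.

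**Assumptions.** Residual SD 0.5 log10 (0.4–0.6 where shown); share positive p from 0 to 10%; Day 36 shift d of 0.3 to 1.0 log10; age slope 0.05 or 0.10 log10 per decade.

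**1. Precision of one GMT ratio with no positives.** SE = SD × √(2/45) = 0.5 × 0.2108 = 0.1054. The 95% CI is the estimate ×/÷ 10^(1.98 × 0.1054) = 1.62. At SD 0.4 the factor is 1.47; at SD 0.6 it is 1.78.

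**2. Gain from baseline status.** R² = p(1−p)d² / [p(1−p)d² + SD²], and adjustment multiplies the SE by √(1 − R²). At SD 0.5:

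- p = 0: R² = 0, no gain.
- p = 1%, d = 1.0: R² = 0.038, SE falls 1.9%.
- p = 2%, d = 0.5: R² = 0.019, SE falls 1.0%.
- p = 2%, d = 1.0: R² = 0.073, SE falls 3.7%.
- p = 5%, d = 0.5: R² = 0.045, SE falls 2.3%.
- p = 5%, d = 0.8: R² = 0.0304/0.2804 = 0.108, SE falls 5.6%.
- p = 5%, d = 1.0: R² = 0.0475/0.2975 = 0.160, SE falls 8.3%.
- p = 10%, d = 1.0: R² = 0.265, SE falls 14%.

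A simulation using the Day 1 titre itself (45 per group, SD 0.45, four sites) gave variance reductions of 10% and 15% at p = 5% with d = 0.8 and 1.0. As SE these are 1 − √0.90 = 5.1% and 1 − √0.85 = 7.8%.

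On the interval scale, for p = 5% and d = 1.0, the unadjusted SD is √(0.25 + 0.0475) = 0.545 and the SE is 0.1150. The factor is 10^(1.98 × 0.1150) = 1.69, against 1.62 after adjustment.

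**3. Gain from age.** Taking age as uniform from 18 to just under 56, the variance is 3.8²/12 = 1.203 decades². A slope of 0.05 gives R² = 0.0030/0.2530 = 0.012, so SE falls 0.6%. A slope of 0.10 gives R² = 0.0120/0.2620 = 0.046, so SE falls 2.3%.

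**4. Both covariates, simulated SE ratio (adjusted/unadjusted).**

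- No positives, no age effect: 1.004.
- 2%, d = 0.5, slope 0.05: 0.994.
- 5%, d = 0.5, slope 0.05: 0.981.
- 5%, d = 1.0, slope 0.05: 0.927.
- 10%, d = 1.0, slope 0.10: 0.865.

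**5. Imbalance.** Three extra positives in one group of 45 move the GMT ratio by 10^(3d/45): 1.05 at d = 0.3, 1.08 at d = 0.5, 1.17 at d = 1.0. With 3 positives among 135 (about 2%), a gap of at least 3 between the highest and lowest group means all three fall in one group: probability 3 × C(45,3)/C(135,3) = 42,570/400,995 = 0.11. With 7 positives (about 5%), the simulated probability of such a gap is 0.50.

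**6. What GMFI already does.** Log10 fold increase is log10 titre minus log10 baseline, so it forces a baseline slope of 1. If every Day 1 value is below the limit and set to 31, the GMFI ratio equals the GMT ratio. Adding baseline as a covariate to a GMFI model lowers the baseline coefficient by 1 and leaves the dose contrasts identical to those of the titre ANCOVA.

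**The case against.** The case for leaving the plan alone has real weight.

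- **The SAP expects almost no positives.** SAP 13.1 says so. A reader might infer from the indexed figures that the SAP anticipates them in material numbers. The figures show only that the possibility was provided for. Exclusion criterion 9 also lets an investigator exclude on a clinically relevant screening finding. This stands, and it keeps the expected gain small.
- **The harm rests on assumptions.** This stands too. No document figure supports any particular prevalence, shift or age slope.
- **Chance imbalance is not bias.** A reader might infer that the Day 36 ratios, or the dose choice, are biased. For the 135 randomised participants the unadjusted estimator is unbiased and its interval covers chance imbalance; a factor of 1.17 lies well inside 1.62. Only the 15 sentinels, allocated without randomisation and not removed by any analysis-set definition, fall outside that argument.
- **Baseline is handled elsewhere.** This is partly right. GMFI is anchored to Day 1, but with a fixed slope: at d = 0.5 it recovered less than half the precision of the ANCOVA (2% against 4% of variance), and it does nothing for age. Figures and Day 1 distribution curves reveal an imbalance without giving an adjusted ratio.
- **It is late to change the model.** A reader might conclude that the ANCOVA should become the main analysis for visits not yet reported. The documents do not support that. SAP 8 says the Part A Day 36 analysis was performed, protocol 16.5 unblinds the study then, and protocol 8.5 reports the high dose as selected. A new main model would be chosen after unblinding, depart from protocol 16.4.2, and put Day 36 and later visits on different footings.
- **Leverage.** With most Day 1 values at one substituted number, the baseline slope would rest on a few positives. That is a further reason to keep the ANCOVA supportive.

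**Conclusion.** The point holds as a modest robustness gap. The primary GMT comparison omits two baseline variables that are scheduled for everyone. With the serostatus stratification dropped and the Day 1 alternative optional, it has no committed protection against an imbalance in baseline positives beyond descriptive figures and the separate GMFI endpoint.

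The precision at stake is nil with no positives and no age effect. It is about 0–2% in SE at the prevalence the SAP expects. Since the SAP gives no number, that range reads negligible as about 1% positive with a shift of up to 1.0 log10, or 2% with a shift of 0.5. It rises to about 5–8% if 5% are positive with a shift of 0.8–1.0 log10. All of these rest on assumed values.

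Nothing here shows that the reported Day 36 comparison is wrong. The study has no formal hypotheses (SAP 2.2), and ANOVA with site is a legitimate prespecified choice. What is missing is a committed check on how far the ratios depend on baseline status.

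**What to change.** - **SAP 8.1, and by reference 8.2.1 and 8.2.4 for post-baseline visits only.** Add an ANCOVA of log10 titre on dose group, study site, Day 1 log10 titre from the same assay, and age. Enter Day 1 neutralisation values below 62 as 31, and Day 1 ELISA values below 50.3 as 25 ELU/mL. Day 1 is left out as an outcome because the model would regress the titre on itself.
- **Reporting.** Show the adjusted GMT ratios beside those of the unadjusted ANOVA on the same values. The Part A run used 58 and 29 for the limit and its substitute, so for Day 36 the companion should be the later run with 62 and 31.
- **Status.** Label it a supportive analysis added after the Part A unblinding, and record it in SAP 13.1.
- **SAP 8.2.3 and 8.2.6.** Leave the GMFI models unchanged, since adding baseline would only reproduce the ANCOVA's dose contrast.
- **SAP 8.** Change the stratified presentation by Visit 1 neutralisation status from *may* to *will*.

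**Cost.** Two of about 130 residual degrees of freedom (135 − 3 dose groups − 3 for an assumed four sites = 129), a little more programming, no new data, and a label that readers will rightly weigh. The rank-based fallback is not affected.

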## **16. STATISTICS**

### **16.1 Sample Size and Power Calculations**

A total of 150 Participants is considered sufficient to obtain initial safety data for VLA2001, especially since inactivated vaccines are a well-established, safe vaccine technology. Fifty Participants per group will allow for 95% confidence that an AE with a true underlying incidence of about 2% would be observed in the present study.

In addition, assuming 10% of Participants with protocol deviations, about 45 Participants per dose group will be evaluable for immunogenicity. This sample size is in a range generally expected to allow selection of an appropriate dose level.

Booster Phase:

For the Booster Phase of this study no formal sample size calculation has been performed and no minimal or maximal number of participants is defined. Based on operational considerations the total number of participants is expected to be up to approximately 80 Participants.

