### **16.4 Methods of Analysis**

A Statistical Analysis Plan (SAP) will be provided describing in more detail, how the study results will be evaluated. The SAP will be finalized prior to the Blind Data Review Meeting for Part A analysis

Data will be summarized by treatment group and, where appropriate, by visit and SARS-CoV-2 baseline serostatus. Descriptive statistics (number of observations, mean, standard deviation, minimum, median, and maximum) will be provided for continuous variables (e.g. age and weight). Frequency counts and percentages will be presented for categorical variables (e.g. gender).

All data exclusions, including premature terminations, will be detailed and tabulated. Data listings will include enrolled Participants.

Baseline characteristics including demographic variables, medical and vaccination history and concomitant medications will be subject to descriptive analyses.

AEs and medical history will be coded using the MedDRA coding dictionary. Concomitant medications (including vaccinations) will be coded using the WHO Drug Dictionary.

More detailed criteria to identify Participants in each analysis set, other research questions of interest not covered in this protocol, the definition of endpoints and details of their calculation, as well as further details on how to deal with missing, unused and spurious data will be covered in the SAP. If a change of the planned analyses is considered necessary after protocol finalization, this will be described and justified in the SAP. If a change is made after the statistical analysis has been performed, this will be described and justified in the CSR.

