### **16.4.1 Primary Safety Endpoint**

The number and percentage of Participants with solicited local and systemic AEs within 7 days after each and after any vaccination will be presented. Differences between the treatment groups will be assessed for significance using Fisher's exact test, a significant overall test will be amended by pair-wise tests.

This analysis will be repeated stratified by baseline SARS-CoV-2 serostatus.

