2.4 TRIAL DESCRIPTION

This is a first-in-human phase I/II study that will evaluate three dose levels of VLA2001 (low, medium, high) for safety, tolerability and immunogenicity in a two-dose schedule in a healthy young adult population aged 18 to 55 years.

The study will be a combined open-label followed by a randomised, double-blind, dose-escalation, multicentre study with three dose groups (low, medium and high dose groups); 50 participants will be recruited to each dose group. The study is conducted in three parts: Part A (Day 1 to Day 36) and Part B (Day 37 to Day 208) followed by the Booster Phase: Part C (Visit 7 to Visit 10). Following an evaluation of Part A data (i.e. data up to Day 36) further clinical studies will be initiated. An additional data analysis will be performed during part B after all Participants have completed Visit 5 (Day 106).

The study will start with an open-label, staggered recruitment for the first 15 participants and subsequently in the blinded part of the study for all remaining 135 participants. Randomization will be done in 1:1:1 fashion for the 3 dose levels.

PART A:

For safety reasons, the first 15 participants will be included into the study in an open-label, not randomized manner following a staggered dose escalation of VLA2001. Dose escalation will be done at a single site to ensure permanent oversight on safety data by one principal investigator during the recruitment of the 15 sentinel participants.

Dose escalation starts with the first vaccination of the first sentinel participant in the low dose treatment group. After vaccination, the first participant of a dosing group will be observed for the development of any acute reaction at the study site for 3 hours after the vaccination procedure. Prior to discharge from the study site, vital signs will be measured and the participant will be instructed to use the eDiary. The next 4 participants of the same dosing group will be vaccinated at least with a one-hour interval between each participant. These 4 participants will be observed for 60 minutes at the study site to monitor for the development of acute reaction. Before discharge, vital signs will be measured and participants will be instructed to use their eDiaries. After confirmation by the investigator, the procedure will be repeated with the first participant of the next dose level. The minimum time before vaccination of a new dose level will be 48 hours.

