13 APPENDICES

13.1 CHANGES TO THE PROTOCOL SPECIFIED ANALYSES

As discussed with the sponsor, the analysis will not be stratified by serostatus for SARS-CoV-2 at screening because the chance that there are seropositive subjects enrolled in the study is negligible due to exclusion criteria #2 as per protocol.

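### SAP 8.1 runs Tukey's HSD only after a significant ANOVA; the protocol sets no such condition, SAP 13.1 does not declare the change, and error control does not need it

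*SAP*

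**What the plan says.** - **Protocol 16.4.2** (and the synopsis, statistical methods) estimates GMTs and GMT ratios from an ANOVA on log10 titres with dose group and site as factors. It then says that Tukey's "HSD test will be applied for pair wise comparisons". No overall test has to be passed first.
- **SAP 8.1** uses the same model but introduces the pairwise step with "If ANOVA suggests dose group differences to be statistically significant then" Tukey's HSD.
- **The SAP 8.1 fallback** for non-normal log titres has the same structure: Kruskal-Wallis first, and the DSCF pairwise procedure only if that is significant.
- **Where the protocol wants a gate, it writes one.** For the Fisher tests of solicited events, protocol 16.4.1 states that "a significant overall test will be amended by pair-wise tests". Protocol 16.4.3.1 and 16.4.3.2 have the equivalent clause for the other Fisher tests. The Tukey sentence has none.
- **Protocol 16.4** sets the rule for departures: "If a change of the planned analyses is considered necessary after protocol finalization, this will be described and justified in the SAP".
- **SAP 13.1** lists a single change, that "the analysis will not be stratified by serostatus for SARS-CoV-2 at screening". It does not mention the pairwise procedure.

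**The concern.** The two documents would run different tests on the same data whenever Tukey's HSD finds a pair and the F-test does not. The difference concerns a primary endpoint, and the reader is not told of it although the protocol says it must be explained.

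The gate also has no clear purpose. An overall test is useful in front of unadjusted pairwise tests. Tukey's HSD is already a simultaneous procedure for all three pairs, so a preliminary F-test can only remove rejections.

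The rule reaches beyond Day 36. SAP 8.2.1, 8.2.3, 8.2.4 and 8.2.6 (titres, fold increase and IgG at other visits) and 8.3.1, 8.3.3, 8.3.4 and 8.3.6 (booster GMTs and fold rises, presented by primary dose group) all take their method from the primary endpoint.

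**Working it through.** **Inputs**
- Group size: the SAP plans that "50 participants will be recruited to each dose group". With 10% protocol deviations, 50 × (1 − 0.10) = 45, which reproduces the protocol's figure that "about 45 Participants per dose group will be evaluable for immunogenicity". Residual df = 3 × 45 − 3 = 132, ignoring site.
- Level: SAP 8.1 writes "significantly different among dose groups at 5% level of significance" for the Kruskal-Wallis test. Using 5% for the ANOVA and Tukey's HSD as well is an assumption, consistent with the 95% CIs.
- Effect and SD: the documents give neither for log10 titre. Effects are therefore assumed, in SD units, and swept over a range.

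**Where the two rules disagree.** Let R be the range of the three group means, q = R / √(MSE/n) and F = n·Σ(mᵢ − m̄)² / (2·MSE). The 5% critical values at df 132 are 3.352 for q (three groups) and 3.065 for F.
- Middle mean halfway between the others: Σ(mᵢ − m̄)² = R²/2, so F = q²/4. At Tukey's threshold F = 3.352²/4 = 2.81, below 3.065. The gate blocks Tukey rejections until q = 2√3.065 = 3.50.
- Middle mean equal to one extreme: Σ(mᵢ − m̄)² = 2R²/3, so F = q²/3. At Tukey's threshold F = 3.352²/3 = 3.75, above 3.065. The gate blocks nothing.

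The gate therefore acts only in a narrow band, and mainly when the observed means rise in roughly equal steps.

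**Size of the effect.** Simulation of group means and pooled variance, 45 per group, true means 0, d/2, d in SD units. Entries are percentages; losses were taken before rounding.

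| d (SD) | Any pair: Tukey alone | Any pair: gated | Loss | High vs low: Tukey alone | High vs low: gated | Loss |
|---|---|---|---|---|---|---|
| 0 (familywise error) | 5.0 | 4.5 | 0.5 | – | – | – |
| 0.30 | 22.2 | 20.9 | 1.3 | 17.5 | 16.6 | 0.9 |
| 0.50 | 54.3 | 52.6 | 1.7 | 50.2 | 48.7 | 1.5 |
| 0.55 | 63.0 | 61.4 | 1.7 | 59.5 | 58.0 | 1.5 |
| 0.70 | 84.5 | 83.5 | 1.1 | 82.8 | 81.8 | 1.0 |
| 0.80 | 93.0 | 92.4 | 0.6 | 92.1 | 91.5 | 0.6 |

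**Sensitivity**
- Other group sizes (15, 50, and unbalanced 40/45/50) and other dose-response shapes: the largest any-pair loss is 1.5 to 1.7 points. For high vs medium it is at most 0.8.
- Four df removed for site (an assumed number): 54.3% vs 52.6% at d = 0.50, unchanged.
- Booster phase: up to about 80 participants, so 80/3 ≈ 26 per group if evenly spread (assumption). With means 0/0.35/0.7 SD, any-pair power is 59.2% alone and 57.5% gated.
- Error control without the gate: Tukey's HSD alone stays at 5.0% under the global null, balanced or 40/45/50. When only the high dose differs, its familywise error is about 1.9%.

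**The case against.** **The protocol is silent on sequence, and it leaves detail to the SAP.** Protocol 16.4 does say the SAP will give more detail, and an overall test followed by pairwise tests is the protocol's own habit for Fisher's test. But the habit is spelled out there and absent from the Tukey sentence. The addition also changes which tests are run, so it is more than detail. At the least it belongs in SAP 13.1.

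**The effect is very small and rests on assumed effects.** This stands. SAP 2.2 states no formal hypotheses, and a familywise error of 4.5% rather than 5.0% is harmless in an estimation-oriented phase I/II study.

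**Two stronger readings are tempting, and the documents support neither.**
- A reader might infer that a narrow miss on F leaves no pairwise comparison at all. SAP 8.1 obtains least squares mean differences with 95% CIs from the ANOVA and back-transforms them before the condition appears. On the log scale these are GMT ratios. Only the Tukey test is withheld.
- A reader might infer that dose selection is at risk. Protocol 8.5 reports that the Day 36 analysis is complete and the high dose was chosen for its better immunogenicity with similar safety. SAP section 8 also refers to that analysis as done. Editing the SAP cannot alter the choice, and a gate that acts only on marginal results is unlikely to have influenced it.

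**Changing the test rule now is a post-unblinding edit.** This also stands. Under protocol 16.5 the study is unblinded at the Part A analysis, so the change must be dated and explained and confined to analyses still to be run.

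**Conclusion.** The point holds as a minor one. The SAP adds a condition that the protocol does not contain and does not declare it, contrary to protocol 16.4; this part rests on the texts alone. The condition gives no error control that Tukey's HSD lacks. Its cost is at most about 1.7 points of any-pair power and 1.5 points for high vs low. The loss peaks where power is roughly 45% to 65% and is about 1 point or less above 85%. These figures assume a 5% level, normal log10 titres, about 45 per arm and the standardised effects shown, none of which the documents fix apart from the group size. The practical gain lies in the later titre, fold-increase, ELISA and booster analyses and in a traceable record.

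**What to change.** 1. In SAP 8.1 replace the conditional sentence with: *Tukey's HSD will be applied to the three dose pairs whatever the result of the overall ANOVA.* Let this govern every analysis still to be run that inherits the method: 8.2.1, 8.2.3, 8.2.4, 8.2.6, 8.3.1, 8.3.3, 8.3.4 and 8.3.6.
2. Treat the fallback the same way: report DSCF whatever Kruskal-Wallis shows. Otherwise pairwise testing would be ungated for normal data and gated for non-normal data.
3. In SAP 13.1 record that the Part A Day 36 analysis was specified with the gate, and date the change.
4. If Tukey-adjusted intervals for the GMT ratios are shown, label them as an addition. Protocol 16.4.2 asks for 95% CIs and does not call for adjusted ones.

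If the sponsor prefers to keep the gate, an entry in SAP 13.1 describing and justifying it would meet protocol 16.4, at the small power cost shown.

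The cost is a few SAP sentences and a small programming change, with no new data and familywise error still at 5%. The one real burden is explaining an edit made after unblinding, which the entry in 13.1 covers.
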